The PI will prepare a report on data and safety parameters for the Independent Monitor for the first ten subjects or annually, whichever comes first. The Independent monitor will provide a written monitoring report to be submitted to the IRB at the time of continuing review.

c. Criteria for stopping the study or suspending enrollment or procedures The Independent Monitor and IRB will determine if changes are needed for the research to continue or if it will be closed. Any changes required as conditions for resuming the research must be submitted as an amendment and IRB-approved before the changes can be implemented. The PI/Independent Monitor and IRB will determine if changes are needed for the research to continue or if it will be closed. Any changes required as conditions for resuming the research must be submitted as an amendment and IRB-approved before the changes can be implemented.

16. Quality Assurance

a. Quality assurance monitor

Quality assurance will be monitored by the PI, The research team and the NIMH Office of Regulatory Compliance (ORO).

b. Quality assurance plan

ORO monitors intramural research studies to ensure compliance with GCP, organizational policies and regulations. Audit frequency is determined by the ORO SOP based on the study level of risk. Results of ORO audits are provided to the PI, The Clinical Director and the CNS IRB. As an IND study, this protocol will be subject to GCP audits at study initiation and after the first enrolled subject. Timing of subsequent review will be established by the ORO but no less frequent than every other year.

17. Reporting of Unanticipated Problems, Adverse Events and Protocol Deviations

Reportable events for this protocol will be tracked and reported in compliance with Policy 801.

18. Alternatives to Participation

Subjects do not receive any treatment in this study or forego any treatment in order to participate in this study. The alternative, therefore, is not to participate.

19. Privacy

All research activities will be conducted in as private a setting as possible.

20. Confidentiality

a. For research data and investigator medical records

Data will be stored using codes that we assign. Data will be kept in passwordprotected computers. Only study investigators will have access to the data. The results of urine drug screen will be in the NIH Medical Record.

This study collects sensitive information on drug and alcohol use. The PI will train study staff regarding obtaining and handling potentially sensitive and private information about co-workers through staff discussions and written branch/section procedures.

b. For stored samples

Samples are not stored.

c. Special precautions

Samples and data will be stored using codes that we assign. Data will be kept in password-protected computers. Samples will be kept in locked storage. Only study investigators will have access to the samples and data. De-identified results from clinical trials will be posted on cctrials.gov.

Any clinically relevant results will be returned to the participant.

21. Conflict of Interest

a. Distribution of NIH guidelines

NIH guidelines on conflict of interest have been distributed to all investigators.

b. Conflict of interest

There are no conflicts of interest to report.

c. Role of a commercial company or sponsor

Commercial company or sponsor is not involved.

22. Technology Transfer

No Technology Transfer is involved in this study.

23. Research and Travel Compensation

Subjects will be compensated for time and research-related inconveniences. Reimbursement is based on NIH standards for time devoted to the research project. This study will also provide travel compensation based on NIH standards. Subjects will be paid for each portion of the study they have completed whether or not they opt for early withdrawal from participation. MAS patients and controls may receive a maximum of \$1190 and \$930, respectively. Subjects will be paid for each portion of the study they have completed whether or not they opt for early withdrawal from participation. Payment will be sent after participation has been completed. Employees and staff who participate during work hours must have permission from their supervisor. NIH employees must either participate outside of work hours or take leave in order to receive compensation.

Schedule of Visits and Remuneration

	Inconvenience Units	Inconvenience Remuneration	Time (hours)	Time Remuneration	Total Remuneration
I/2-24 1	Units	Remuneration	(nours)	Kemuneration	Remuneration
Visit 1: screening (patient only)*					
Medical history, physical exam, EKG, and lab tests if not	2	\$20	2	\$30	\$50
obtained in prior six months					
Neuropsych Testing	4	\$40	3	\$40	\$80
Visit 2**					
Pregnancy test***	1	\$10			\$10
MRI	8	\$80	2	\$30	\$110
Visit 3**					
Pregnancy test***	1	\$10			\$10
Brain PET scan	15	\$150	5	\$60	\$210
Venous catheter	3	\$30			\$30
Arterial catheter	7	\$70			\$70
Movement restriction	1	\$10			\$10
Visit 4**					
Pregnancy test***	1	\$10			\$10
Whole body PET scan	15	\$150	4	\$50	\$200
Venous catheter x2	6	\$60			\$60
Movement restriction	1	\$10			\$10
Visit 5**					
Roflumilast admin	1	\$50			\$50
Pregnancy test*** †	1	\$10			\$10
Whole body PET scan	15	\$150	4	\$50	\$200
Venous catheter x2 ^{††}	6	\$60			\$60
Movement restriction	1	\$10			\$10
Total	89	\$930	20	\$260	\$1190

*Screening will be repeated for subjects with MAS if no information is available within 6 months under 98-D-0145. Healthy volunteers will be screened under protocol 01-M-0254 or 17-M-0181.

**The order of visits 2, 3, 4 and 5 may change depending on the availability of the scanners.

***Pregnancy testing for women of childbearing potential

[†]The pregnancy test for the second whole body PET scan will not be conducted if the scan takes place the same day as the baseline whole body scan.

^{††} Subjects will not receive compensation for placement of catheters if blocked scan occurs on the same day as baseline scan and catheters are already in place. Note: Some visits may be combined.

24. References

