- 7. Inability to lie flat on camera bed for about two and a half hours.
- 8. Pregnancy or breastfeeding.
- **9.** NIMH employees/staff and their immediate family members will be excluded from the study per NIMH policy.

10. Currently taking a PDE4 inhibitor (such as roflumilast or apremilast), a drug that inhibits or induces cytochrome P450 (such as rifampicin or erythromycin), or oral contraceptives containing gestodene and ethinyl estradiol (such as Minulet and Femodene).

Healthy Subjects

- 1. Serious medical conditions, which may interfere with study procedures. Such conditions include but not limited to clinically marked dysfunction of liver or kidney, which may delay clearance of $[^{11}C](R)$ -rolipram.
- 2. Clinically significant laboratory abnormalities that may interfere with the PET measurement or affect safety of the participant during this study.
- 3. Personal history of any DSM Axis I disorder.
- 4. Positive HIV test.
- **5.** Head trauma resulting in a period of unconsciousness lasting longer than one hour.
- 6. Metallic foreign bodies that would be affected by the MRI magnet, or fear of enclosed spaces likely to make the subject unable to undergo an MRI scan.
- 7. Recent research-related exposure to radiation (i.e., PET from other research) that, when combined with this study, would be above the allowable limits.
- 8. Inability to lie flat on camera bed for about two and a half hours.
- 9. Pregnancy or breastfeeding.
- 10. Current substance use disorder based on DSM.
- **11.** NIMH employees/staff and their immediate family members will be excluded from the study per NIMH policy.
- **12.** Currently taking a PDE4 inhibitor (such as roflumilast or apremilast), a drug that inhibits or induces cytochrome P450 (such as rifampicin or erythromycin), or oral contraceptives containing gestodene and ethinyl estradiol (such as Minulet and Femodene).

4. Study Design and Methods

a. Study overview

This study will have two populations: subjects with MAS and healthy control subjects. Both MAS subjects and healthy controls will have up to three PET scans. All subjects will be given the option to have the following: one brain scan, one baseline whole-body scan, and one blocked whole-body scan after roflumilast administration. The two whole body scans can be performed on the same day or on separate days. The blocked whole body scan will be performed approximately 1-2 hours after the administration of 500 μ g roflumilast P.O.

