To achieve the goals of this exploratory study, we request a total of 35 subjects: ~10 MAS subjects to undergo brain PET scan, ~10 MAS subjects to undergo whole body PET, and 15 healthy controls to undergo a brain scan and/or a whole body PET scan. By limiting subjects with MAS to those who have craniofacial fibrous dysplasia and neuropsychological symptoms, we expect to increase the likelihood of detecting changes in PET in this small sample size. To limit the number of study participants, all MAS and healthy subjects will be asked if they would be willing to have both brain and whole body PET scans. A smaller number of 15 healthy subjects are requested because healthy subjects are more likely to have both brain and whole body scans. Our previous study of [¹¹C](*R*)-rolipram brain scans in healthy subjects found that the coefficient of variation (SD/mean) of VT was 19%. Based on the activation of G_sa, we hypothesize that MAS patients will show increased rolipram binding for whichever one-sided test is appropriate. Assuming a 20% dropout from 10 subjects (thus, eight subjects per group) plus a 19% coefficient of variation (SD/mean) will provide a power of 0.80 to detect a 19% increase.

11. Human Subjects Protection

a. Subject selection

The study will be open to all racial and ethnic groups and will not target any particular group. Healthy volunteers will be recruited to match the patient group for age. Those who are HIV positive are excluded because the possible viral effects on the brain could interfere with interpretation of the outcome of the study.

b. Justification for exclusion of children

We will exclude children younger than 18 years of age to avoid radiation exposure to minors because the risks of radiation exposure outweighs the benefits.

c. Justification for inclusion of other vulnerable subjects

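### The control payment maximum of $930 in Section 23 does not match the section's own table, which pays a control up to $1060

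*Combined protocol and SAP*

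**What the plan says.** Section 23 (Research and Travel Compensation) opens with the principle: "Subjects will be compensated for time and research-related inconveniences". It then gives the ceilings: "MAS patients and controls may receive a maximum of \$1190 and \$930, respectively". It says twice that "Subjects will be paid for each portion of the study they have completed whether or not they opt for early withdrawal from participation".

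One table, the Schedule of Visits and Remuneration, follows for both groups. The label of its first block begins "Visit 1: screening (patient only", and no other block is limited to one group. A footnote explains why controls have no first visit here: "Healthy volunteers will be screened under protocol 01-M-0254 or 17-M-0181". The bottom line, in the order units, inconvenience pay, hours, time pay and total, reads "Total 89 \$930 20 \$260 \$1190".

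Controls can reach every later visit. Section 4a says that "Both MAS subjects and healthy controls will have up to three PET scans", Section 4d lists the blocked scan for controls, and Section 4d.iv requires a brain MRI of all subjects unless a suitable one was done in the prior year.

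**The concern.** The patient ceiling equals the table total, so a reader expects the control ceiling to be that total less whatever controls cannot receive. It is not. The printed $930 is lower than the sum of the visits open to a control, although Section 23 promises payment for each completed portion and nowhere sets a lower rate for controls.

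At stake is an operative payment figure. Staff who pay by the table can exceed the stated maximum, and staff who respect the maximum can leave completed procedures unpaid. The controls affected are those who undergo the most procedures, in a study that Sections 12 and 13 describe as more than minimal risk without direct benefit.

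**Working it through.** **Inputs.** All amounts come from the Section 23 table and its footnotes. The MRI waiver comes from Section 4d.iv, and the two-hour duration for controls from the procedure list in Section 4d.

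**Step 1: reproduce the patient maximum.**

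| Visit | Rows added | Total |
|---|---|---|
| 1 (patients only) | $50 + $80 | $130 |
| 2 (MRI) | $10 + $110 | $120 |
| 3 (brain PET) | $10 + $210 + $30 + $70 + $10 | $330 |
| 4 (baseline whole body) | $10 + $200 + $60 + $10 | $280 |
| 5 (blocked whole body) | $50 + $10 + $200 + $60 + $10 | $330 |

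$130 + $120 + $330 + $280 + $330 = $1190. The patient figure reproduces exactly. The other columns also add up: 89 units, $930 inconvenience pay, 20 hours, $260 time pay.

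**Step 2: control maximum on the same basis.** $1190 - $130 = $1060, made up of $870 inconvenience pay ($930 - $60) and $190 time pay ($260 - $70). The stated $930 is $130 lower, and 130/1060 = 12%.

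**Step 3: could $930 be some other control total?** Sums of three control visits are $730 (Visits 2, 3, 4), $730 (2, 4, 5), $780 (2, 3, 5) and $940 (3, 4, 5); all four visits give $1060. No set of whole visits gives $930, and neither does control inconvenience pay alone ($870).

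**Step 4: controls who have all three PET scans.** Each pregnancy test pays $10, and only to women of childbearing potential. A same-day blocked scan removes the Visit 5 pregnancy test ($10) and catheter payment ($60). A waived MRI removes Visit 2 ($120, or $110 where no pregnancy test is paid).

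| Pregnancy tests paid | Whole-body scans | With paid MRI | MRI waived |
|---|---|---|---|
| Yes | separate days | $1060 | $940 |
| No | separate days | $1020 | $910 |
| Yes | same day | $990 | $870 |
| No | same day | $960 | $850 |

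All four cases with a paid MRI exceed $930. Of the four with a waived MRI, only the $940 case does.

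**Step 5: controls without the blocked scan.** The most they can receive is $120 + $330 + $280 = $730, well under $930. The conflict is therefore confined to controls who add the blocked scan.

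**Step 6: the hours paid for the blocked scan.** The table pays 4 hours ($50) for the Visit 5 scan. Section 4d lists two hours for controls and five for patients. Elsewhere in the table 2 hours earn $30. At that rate each total in Step 4 falls by $20: the control maximum becomes $1060 - $20 = $1040, and the lowest total with a paid MRI becomes $960 - $20 = $940. Both still exceed $930. With the MRI waived, the highest becomes $940 - $20 = $920, so no waived-MRI case would exceed it.

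**The case against.** The strongest reply is that little depends on this figure. The blocked scan is optional, and the pay-per-portion rule suggests that a control would in practice be paid in full. Where the MRI is waived the ceiling is seldom reached. This stands as a limit on the size of the point, but it does not remove the mismatch: a stated maximum has to cover the highest case that the schedule allows.

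Four stronger readings are tempting, and the documents do not support them.

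- *That $930 was copied from the inconvenience column.* The match is exact, but $930 also equals $1190 - 2 x $130, which is Visit 1 deducted twice. The plan does not say how the figure arose.
- *That the roflumilast row is a second arithmetic error.* It carries 1 unit and $50, while every other row pays $10 per unit, so 89 units at $10 would give $890. But no text sets a rate per unit, and the row is carried correctly into both printed totals. It merits a query and no more.
- *That the ceiling undermines the choice of 15 controls.* Section 10b says: "A smaller number of 15 healthy subjects are requested because healthy subjects are more likely to have both brain and whole body scans". That concerns brain plus whole-body scans, which pay at most $730 with the MRI. The blocked scan is not part of that reasoning.
- *That controls will be underpaid, or that $1060 is certainly the intended figure.* Nothing says that any control will be held to $930, and the two-hour entry in Section 4d leaves $1040 possible. That entry does not settle the matter either: the same list gives the MRI one hour where the table pays two, so paid hours do not simply follow listed durations.

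**Conclusion.** The control maximum is wrong as written. On the table as it stands it should be $1060, so $930 is $130 too low. A control with a paid MRI and all three PET scans earns $960 to $1060 and always passes the stated maximum; with the MRI waived, one case in four does.

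The $1060 assumes four paid pregnancy tests, whole-body scans on separate days and the table's four paid hours for the blocked scan. The first two assumptions also underlie the patient figure of $1190. The finding does not depend on any of the three, because every variant with a paid MRI stays above $930.

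The consequence is administrative. It is at most $130 per control who adds the blocked scan, or 15 x $130 = $1950 if all 15 accrued controls reached the maximum. No endpoint, analysis or sample-size argument changes.

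**What to change.** First reconcile the four hours that the table pays for the blocked scan with the two hours that Section 4d lists for controls. Then restate the control maximum in Section 23 to match: $1060 if the table stands, $1040 if controls are to be paid for two hours at the table's rate. Add a control total line under the table so that both ceilings can be read from it. The consent forms were not available for this review; if the control forms repeat $930, correct them too.

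Separately, ask why roflumilast administration counts as 1 unit but pays $50. If a flat payment is intended, a footnote would settle it.

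The cost is a wording amendment and, where needed, revised control consent forms. Payment by the table adds at most $130 per affected control over the stated ceiling.
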